8.1.4 INCREMENTAL COSTS AND GAINS OF THE SEARCH YOUTH INTERVENTION

We will use rigorous methods to determine costs of the SEARCH Youth intervention and assess its efficiency and cost-effectiveness as cost per participant, cost per additional participant with viral suppression and cost per DALY gained. We will use standard micro-costing techniques and time-in-

motion (T&M) studies to measure the cost of optimized testing and each component of the SEARCH Youth intervention.

Costs Analysis

We will assess costs at least twice in each health facility: once before and once after adoption of the SEARCH Youth intervention, in order to estimate incremental costs of SEARCH Youth implementation and to compare costs of the intervention to standard of care. “Economic” costs (the true value of resources consumed or “opportunity cost”) will be assessed by identifying the value of subsidized or donated resources with information from data bases (e.g. wage rates) and donors, and, as needed, three price quotes from appropriate market sources.

Health Effects

To quantify health effects, we will use directly measured health-related study outcomes (e.g. viral suppression). Second, we plan to integrate the health impact of achieving viral suppression using disability-adjusted life years (DALYs), including years of life gained and the collective disability effects of living with HIV. We might be estimated as DALYs gained for the short term (during the trial) and the long-term (5, 10, and 20 years) using data from the trial, as well as morbidity and mortality attributed to un- or partially- treated HIV disease.

8.1.5 ASSESSMENT OF ALCOHOL USE AND ITS EFFECT ON VIRAL SUPPRESSION

Assessment of alcohol use among SEARCH-Youth intervention participants may include use of surveys, validated alcohol self-report tools (e.g. AUDIT-C), and alcohol biomarker measurement (e.g. phosphatidylethanol [PEth], a blood-based biomarker). We will characterize alcohol use and assess the relationship with viral suppression, accounting for sex and life-stage using the data obtained in the SEARCH Youth intervention (see section 6.1.1).

Participants who are enrolled in the SEARCH Youth RCT at clinic sites randomized to the intervention will be eligible to participate. Potential participants will be approached to discuss the study and, if interested, provide informed consent.

Initial visit: We will administer a questionnaire that will measure alcohol use by self-report and will explore multiple domains of influence on alcohol use and related behaviors. We will collect a blood sample to measure PEth, a biomarker of alcohol use.

Subsequent visits: We will reassess alcohol use and/or risk factors by survey every 3 months for at least 12 months. We will collect blood samples for PEth measurement 12 months after the initial PEth sample is collected.

8.1.6 ASSESSMENT OF INFANT OUTCOMES

Infants of participants enrolled in the SEARCH Youth RCT at clinic sites randomized to either the intervention and control arms, born during the study period, will be eligible to participate. Women who have delivered will be approached for this data collection and, if interested, provide informed consent. A waiver of informed consent for recruitment purposes will be utilized in order to assess the completeness of standard care clinic records prior to meeting with participants. No data will be recorded before informed consent is obtained.

Infant outcomes will be characterized using data collected by the study team using the medical records of the child in the exposed infant care programs and by maternal report. The outcomes of interest include participation in scheduled visits in the HIV-exposed infant programs, receipt of antiretroviral medications as prophylaxis (drugs and duration), duration of breast feeding, HIV test results and mortality, at 1 and 2 years of life (for those who reach that duration during the study period).

In addition, viral load (VL) testing may be performed on participating mothers prior to transitioning off study if they do not have recent VL testing in the medical record. Staff may also help facilitate standard of care HIV testing of the infants if they have not completed the country's Early Infant Diagnosis (EID)/HIV Exposed Infant (HEI) program; there will be no extra testing of infants for the purpose of this study.

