4. To characterize alcohol use and investigate its impact on viral suppression , we will measure alcohol use by self-report and blood-based biomarker and assess associated risk factors in participants randomized to the intervention at scheduled study visits	4.a. Self-reported alcohol use (by Alcohol Use Disorders Identification Test-Consumption (AUDIT-C) score) 4.b. Biomarker-measured alcohol use (by phosphatidylethanol (PEth))	Knowing the relative contribution of alcohol use to viral non-suppression may inform future implementation and refinement of the intervention
5. To evaluate the effect of the SEARCH Youth intervention on HIV-free survival among infants born to participants	5.a. Proportion of infants who remain alive and HIV-free at 1 and 2 years 5.b. Proportion of infants who complete country-specific testing programs for HIV-exposed infants	A larger portion of women deliver children during this age period. The SEARCH youth intervention could improve outcomes by reducing vertical transmission via higher rates of maternal virologic suppression, and increased participation in exposed infant follow up programs.

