9.4 STATISTICAL ANALYSES

9.4.1 GENERAL APPROACH

The primary analysis of the full RCT will be an adjusted comparison of the proportion of AYAH with HIV virologic suppression (HIV-1 RNA copies<400/mL) at 2 years on study between those enrolled at clinics randomized to the intervention condition (n=14 clinics) versus those enrolled at clinics randomized to the control condition (n=14 clinics). To identify mechanisms of action and barriers and facilitators of the study intervention implementation we will examine emergent qualitative themes (perceived benefits, acceptability, gender and life-stage issues, reduced burdens, improved communication, etc.), and for each

of the individual components of the intervention to identify which components worked and did not work and for whom. The incremental costs and gains associated with the intervention will be estimated using micro-costing, time-and-motion (T&M) studies, calculation of disability-adjusted life years (DALYs) gained, estimation of efficiency (cost per patient, costs per additional patient with viral suppression), cost-effectiveness analysis (cost per DALY gained). The efficacy of testing and linkage strategies will be estimated using yield and proportion who link to treatment clinics. Alcohol use patterns will be described and life-stage-specific, and sex-specific prevalence of each pattern will be calculated. The effect of alcohol use on viral non-suppression (HIV-1 RNA copies ≥ 400 c/mL) at 1 year will be estimated using causal inference techniques by comparing the proportion of AYAH with viral non-suppression between those with no alcohol use and those with various patterns of use. The effect of intervention on infants born to participants will be examined through (i) the proportion who remain alive and HIV-free at 1 and 2 years, and (ii) the proportion of who complete their testing programs for HIV-exposed infants.

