9.4.3.6 ASSESSMENT OF INFANT OUTCOMES

Primary Research Question: Does the SEARCH Youth intervention result in a higher rate of HIV-free survival? We will also investigate potential steps in the causal pathway, including participation in HIV-exposed infant care programs, receipt of antiretroviral medications, and duration of lactation.

Analytic Approach: We will compare the proportion of infants who remain alive and have HIV-free at 1 and 2 years of life between randomized arms using the Two-Stage approach, described in section 9.4.2. We will also investigate the intervention effects on elements of postnatal care including the rates of participation in HIV-exposed infant care programs, receipt of antiretroviral medications (agents and durations), and duration of lactation.

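### Staff may help infants in either arm to the HIV testing whose completion is endpoint 5.b, and no rule separates facilitated from unassisted completion

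*Protocol*

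**What the plan says.** Three parts of the Protocol bear on this.

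- **The endpoint.** Section 3 lists 5.b as "Proportion of infants who complete country-specific testing programs for HIV-exposed infants". Section 9.4.1 names it, alongside HIV-free survival, as one of two ways of examining the intervention's effect on infants.
- **The study action.** Section 8.1.6 covers infants of mothers at clinics "randomized to either the intervention and control arms, born during the study period, will be eligible to participate". It then allows that "Staff may also help facilitate standard of care HIV testing of the infants if they have not completed" the national early-diagnosis (EID/HEI) programme, and adds that "there will be no extra testing of infants for the purpose of this study". No arm restriction is placed on the help.
- **The data and the analysis.** Infant outcomes are gathered "using the medical records of the child in the exposed infant care programs and by maternal report". Section 9.4.3.6 says "We will also investigate the intervention effects on elements of postnatal care including the rates of participation in HIV-exposed infant care programs", together with antiretroviral receipt and length of lactation. It does not name programme completion and has no rule for facilitated tests.

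Section 8.1.6 also lets staff check how complete the clinic records are before they meet the mother, but nothing may be recorded until she consents. It does not make that earlier status the endpoint. SAP section 7.1 leaves infant HIV-free survival to a separate analysis plan, which is not among the documents.

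**The concern.** What triggers the help is the very state that 5.b counts as failure. The sentence ruling out study-only tests does not keep the two apart. It means that a facilitated test is an ordinary programme test, and so may enter the same medical record from which outcomes are read.

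Section 3 gives two routes by which the intervention could benefit infants: better maternal suppression and greater use of exposed-infant follow-up. Endpoint 5.b is the listed endpoint closest to the second. If completions prompted by the study are mixed unmarked with those reached in ordinary care, the arm proportions no longer describe ordinary care, and their difference no longer isolates the effect of SEARCH Youth.

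**Working it through.** The documents give no rate, effect size, power or number of infants for 5.b, so there is no stated figure to reproduce. The check is algebra with assumed rates.

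**Set-up.** Let p0 and p1 be unassisted completion in control and intervention. Let f0 and f1 be the shares of non-completers who complete because staff helped. Suppose that facilitated tests count.

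- Observed completion in an arm = p + f(1-p). This is never below p, so help can only raise it.
- Observed difference = (p1-p0) + f1(1-p1) - f0(1-p0).
- If f0 = f1 = f, this reduces to (1-f)(p1-p0).

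**Equal help, assumed 60% v 75%**

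| f | Control | Intervention | Difference (points) | Risk ratio |
|---|---|---|---|---|
| 0 | 60% | 75% | 15 | 1.25 |
| 0.25 | 70% | 81.25% | 11.25 | 1.161 |
| 0.50 | 80% | 87.5% | 7.5 | 1.094 |
| 0.75 | 90% | 93.75% | 3.75 | 1.042 |
| 1.00 | 100% | 100% | 0 | 1.00 |

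At f = 0.50, two other assumed pairs behave in the same way: 50% v 65% goes from 15 to 7.5 points, and 80% v 90% from 10 to 5.

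**Unequal help, assumed 60% v 75%**

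- f0 = 0.2, f1 = 0.8: control 0.60 + 0.2 × 0.40 = 68%; intervention 0.75 + 0.8 × 0.25 = 95%. The difference is +27 points.
- f0 = 0.8, f1 = 0.2: control 0.60 + 0.8 × 0.40 = 92%; intervention 0.75 + 0.2 × 0.25 = 80%. The difference is -12 points.

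**No true difference, assumed 70% in both arms.** Shares of 0.2 and 0.5 give 0.70 + 0.2 × 0.30 = 76% and 0.70 + 0.5 × 0.30 = 85%. That is a spurious 9-point gap, in favour of whichever arm has the larger share.

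**Where the direction turns.** The difference is enlarged when f1(1-p1) exceeds f0(1-p0), that is, when f1/f0 exceeds (1-p0)/(1-p1). For 50% v 65%, 60% v 75% and 80% v 90% the thresholds are 0.50/0.35 = 1.43, 0.40/0.25 = 1.60 and 0.20/0.10 = 2.00.

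**The case against.** The best defence has five parts.

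1. **The help is optional and limited.** The text has staff helping an infant to standard testing, not finishing a programme on the infant's behalf. A reader might infer that staff complete the missing testing. The wording does not support that, and if help is rare the effect is small. This stands as a limit on size, but discretion also means that uptake may differ by clinic and arm.
2. **Dilution is not guaranteed.** A reader might infer that the arm difference must narrow, because the arm with more incomplete infants gets more help. That follows only if help succeeds about equally in both arms, which nothing in the documents states. This stands: the direction is unknown in general.
3. **Other measures remain.** A reader might infer that the trial could no longer tell whether infant follow-up improved. That goes too far. Section 8.1.6 collects attendance at scheduled programme visits, and section 9.4.3.6 compares programme participation between arms. The problem concerns 5.b.
4. **The timing may be harmless.** Section 8.1.6 looks at infant outcomes at one and two years of life and allows a look at the records before contact. The facilitation sentence follows one about maternal testing near the end of participation. All this is compatible with status being fixed before help, but none of it says so.
5. **The separate infant plan may hold a rule.** It may, and this cannot be checked. Such a plan could exclude facilitated tests only if they can be identified in the data, and the Protocol does not require that they be marked.

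Excluding facilitated tests also has a difficulty of its own. Some of those infants would have completed unaided. In intervention clinics, too, help from the clinic's own provider may be part of the intervention, and removing it would take out real effect from one arm only.

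**Conclusion.** The point holds in a limited form. A permitted study action, open to both arms, can change the quantity that 5.b measures, and the available documents have no cut-off, flag or counting rule to separate facilitated from unassisted completion.

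If facilitated tests count, 5.b is raised in each arm. The difference shrinks by the factor (1-f) if help succeeds equally, and is biased in an unknown direction if it does not. The size cannot be stated from the documents, since both the completion rates and the shares helped are assumptions. The conclusion also assumes that the unseen infant plan, or the infant data form, does not already deal with the matter.

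The point concerns one component of the fifth secondary objective. It does not touch the primary endpoint or the separate comparison of programme participation. Label: cheap improvement.

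**What to change.** In Protocol sections 8.1.6 and 9.4.3.6, and in the separate infant analysis plan:

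- Score 5.b from the infant's record under one infant-age or review-date rule, the same in both arms, and before any facilitation by study outcome-assessment staff. Help from the clinic's own providers in the course of care should not be treated as such facilitation.
- Record a flag and a date for each facilitated test.
- Let facilitated results inform HIV status for endpoint 5.a.
- Report the number of infants facilitated, by arm.
- Give the version counting all completions as a sensitivity analysis.

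Facilitation itself is unchanged. The cost is a sentence or two of text, one flag-and-date field on the infant form and one further analysis. The main version will show a lower completion figure. In each arm it is a lower bound on unassisted completion, because some helped infants might have completed unaided. The all-completions version gives the matching upper figure, provided that help never prevents completion.

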8.1.7 ASSESSMENT OF MENTAL HEALTH

A subset of study participants will take part in a one-time survey on symptoms of mental health and life event issues during a visit at the study clinic or by phone. The standard mental health assessment tool Patient Health Questionnaire (PHQ-9) will be administered to participants who take part, along with additional questions on major life events and pressures.

Potential participants will be approached to discuss the survey in the study clinic or by phone call and, if interested, be asked to provide verbal consent to take part. A subset of participants enrolled in the SEARCH Youth RCT at clinic sites randomized to either the intervention or control arms will be eligible to participate.

Participants with score ≥ 5 on the PHQ-9 portion of the survey, or those with a suicidal ideation, have moderate to severe symptoms and will need to be evaluated for therapy including pharmacological therapy. The study coordinator to arrange for urgent referral for mental health care to the regional referral hospital.

8.2 SAFETY ASSESSMENTS

Participants' VL results will be measured regularly as part of the SEARCH Youth intervention. All other safety assessments will be performed according to country standard of care.

8.3 ADVERSE EVENTS AND SERIOUS ADVERSE EVENTS

N/A.

8.4 UNANTICIPATED PROBLEMS

8.4.1 DEFINITION OF UNANTICIPATED PROBLEMS

This protocol uses the definition of Unanticipated Problems (UPs) as defined by the Office for Human Research Protections (OHRP). OHRP considers unanticipated problems involving risks to participants or others to include, in general, any incident, experience, or outcome that meets all of the following criteria:

- Unexpected in terms of nature, severity, or frequency given (a) the research procedures that are described in the protocol-related documents, such as the Institutional Review Board (IRB)-approved research protocol and informed consent document; and (b) the characteristics of the participant population being studied;
- Related or possibly related to participation in the research ("possibly related" means there is a reasonable possibility that the incident, experience, or outcome may have been caused by the procedures involved in the research); and
- Suggests that the research places participants or others at a greater risk of harm (including physical, psychological, economic, or social harm) than was previously known or recognized

8.4.2 UNANTICIPATED PROBLEMS REPORTING

The investigator will report unanticipated problems to the reviewing Institutional Review Board (IRB) and study sponsor. The UP report will include the following information:

- Protocol identifying information: protocol title and number, PI's name, and the IRB project number
- A detailed description of the event, incident, experience, or outcome
- An explanation of the basis for determining that the event, incident, experience, or outcome represents an UP

- A description of any changes to the protocol or other corrective actions that have been taken or are proposed in response to the UP

UPs will be reported using the following timeline:

- UPs that are serious adverse events (SAEs) or protocol violations will be reported to the IRBs within 7-10 working days of the investigator becoming aware of the event (see section 10.1.10 for individual IRB reporting timelines).

8.4.3 REPORTING UNANTICIPATED PROBLEMS TO PARTICIPANTS

Participants will be informed of any UP that changes the study's risk/benefit ratio and/or requires modification to the informed consent. The nature of the UP will determine how and when participants will be notified.

9 STATISTICAL CONSIDERATIONS

9.1 STATISTICAL HYPOTHESES

Primary Endpoint(s): Proportion of study participants with virologic suppression (HIV RNA <400 c/mL) at 2 years of follow-up.

The null hypothesis is there will be no difference in the proportion of participants with virologic suppression at 2 years, between participants who receive the SEARCH Youth intervention and participants in the control arm.

9.2 SAMPLE SIZE DETERMINATION

Because the intervention is delivered at the clinic-level (changing the policies and procedures of the clinic and all clinicians caring for AYAH within the clinic) randomization and evaluation must be done at the clinic-level and incorporate randomization of entire clinics. For the design and power calculations for this study we have taken the rigorous extra step of actually measuring the clustering effect on HIV virologic suppression of clinic level performance for AYAH in 16 clinics in Kenya and Uganda. Using a conservative estimate of the upper 95% CI bound on the measured ICC from the clinic using ICC estimates from both a one-way random-effects model and a one-way Analysis of Variance approaches (ICC=0.055) we have calculated that with 28 clinics (14 randomized to intervention and 14 to control) and an average cluster size of 50-100 AYAH our study would have a 83% or greater power to detect a significant difference between the control and intervention clinics if the proportion with HIV virologic

suppression among AYAH in the control clinics is 64% and the proportion with suppression in the intervention clinics is 88%. In addition, if the study were to lose the ability to evaluate up to 2 clinics due to unforeseen events, the study would still retain 80% power to detect the 64% control vs. 88% intervention difference.

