9.4.2 ANALYSIS OF THE PRIMARY ENDPOINT(S)

Primary Outcome: Proportion of study participants with virologic suppression (HIV RNA <400 c/mL) at 2 years of follow-up

Primary Predictor: Clinic Randomized Arm (intent-to-treat), Intervention or Control.

Analytic Plan: The primary analysis of the full RCT will be an adjusted comparison of the proportion of AYAH with HIV virologic suppression (HIV-1 RNA copies <400 c/mL,) measured at 2 years on study between those enrolled at clinics randomized to the intervention condition (n=14 clinics) versus those enrolled at clinics randomized to the control condition (n=14 clinics). The primary analysis will restrict to participants enrolled prior to December 1, 2019; secondary analyses will include all participants. Viral suppression will be compared between arms using Two-Stage TMLE, an approach that appropriately accounts for the dependence of outcomes within clinics. In the first stage, viral suppression will be estimated for each clinic, using TMLE to adjust for possibly incomplete ascertainment of viral loads. In the second stage will use a cluster-level TMLE to estimate intervention effectiveness by comparing the clinic-specific endpoints between randomized arms, while accounting for the randomization scheme. We will test the null hypothesis that the intervention did not impact viral suppression with a two-sided test at the 5% significance level. To understand effect heterogeneity, we will repeat these analyses within the following pre-specified subgroups: country, baseline care status, baseline viral suppression status, gender, age group, and pregnancy or live birth during the study (among women).

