7.2 Power calculations

Sample size and power calculations were based on the standard formulas for cluster randomized trials with proportion endpoints [11]. We expect these calculations to be conservative, because of the precision gained through covariate adjustment in the analysis as well as our pre-specified choice of a one-sided hypothesis test.

We estimated 28 clinics (14 clinics/arm) would provide 80% power to detect at least a 24% relative increase in viral suppression at 2 years (the primary outcome) from 65% in the standard-of-care, using a two-sided test and assuming a coefficient of variation of $k=0.175$ and at least 50 participants/clinic. As shown in the following Figure, these calculations are fairly insensitive to the number of participants. Under weaker clustering ($k=0.125$) or higher viral suppression in the standard-of-care arm, we anticipate being powered to detect smaller effects.

References

- [1] M. van der Laan and S. Rose. *Targeted Learning: Causal Inference for Observational and Experimental Data*. Springer, New York Dordrecht Heidelberg London, 2011.
- [2] L.B. Balzer, M. van der Laan, J. Ayieko, M. Kamya, et al. Two-stage TMLE to reduce bias and improve efficiency in cluster randomized trials. Technical report, arXiv: <https://arxiv.org/abs/2106.15737>, 2021. URL <https://arxiv.org/abs/2106.15737>.
- [3] M.J. van der Laan, E.C. Polley, and A.E. Hubbard. Super learner. *Statistical Applications in Genetics and Molecular Biology*, 6(1):25, 2007. doi: 10.2202/1544-6115.1309.
- [4] L. Balzer, M. van der Laan, M. Petersen, and the SEARCH Collaboration. Adaptive pre-specification in randomized trials with and without pair-matching. *Statistics in Medicine*, 35(10):4528–4545, 2016. doi: 10.1002/sim.7023.
- [5] A. Benitez, M.L. Petersen, M. van der Laan, N. Santos, E. Butrick, D. Walker, R. Ghosh, P. Otieno, P. Waiswa, and L.B. Balzer. Comparative methods for the analysis of cluster randomized trials. <https://arxiv.org/abs/2110.09633>, 2021.
- [6] J. Neyman. Sur les applications de la theorie des probabilités aux expériences agricoles: Essai des principes (In Polish). English translation by D.M. Dabrowska and T.P. Speed (1990). *Statistical Science*, 5:465–480, 1923.
- [7] D.B. Rubin. Comment: Neyman (1923) and causal inference in experiments and observational studies. *Statistical Science*, 5(4):472–480, 1990.

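### Protocol 9.2 ties 83% power (80% after losing two clinics) to 64% versus 88% suppression, but its own inputs give over 99.9%; the stated pair fits an intervention proportion of about 78%

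*Protocol*

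**What the plan says.** Protocol 9.2 (Sample Size Determination) takes an ICC of 0.055, described as a conservative upper 95% bound from measured clinic data, with 14 clinics per arm and "an average cluster size of 50-100 AYAH". On that basis it says "our study would have a 83% or greater power to detect a significant difference" if the proportion suppressed "in the control clinics is 64% and the proportion with suppression in the intervention clinics is 88" per cent. For the loss of up to two clinics it adds that "the study would still retain 80% power to detect the 64% control vs. 88% intervention difference".

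Section 9.2 does not state the significance level. Protocol 9.4.2 does: the null hypothesis is that the intervention "did not impact viral suppression with a two-sided test at the 5% significance level".

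SAP 7.2 gives a separate calculation for the same 28 clinics: "80% power to detect at least a 24% relative increase in viral suppression at 2 years", starting from 65% in the standard-of-care arm, with a two-sided test, a coefficient of variation k of 0.175 and at least 50 participants per clinic. A 24% relative increase from 65% is 0.65 × 1.24 = 80.6%.

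**The concern.** A 24-point difference is very large for 14 clinics per arm at an ICC of 0.055, so power of only 83% looks too low. The three-point fall when two clinics are lost points the same way. A design with power near 100% loses almost nothing when it goes from 28 to 26 clusters; a fall from 83% to 80% is what one sees when true power is near 83%.

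The stake is how the trial is read. Protocol 9.2 tells the reader that a 24-point gain is what the design can detect with about 80% power, and a smaller or null result could be misjudged against that. SAP 7.2 gives about 80.6 − 65 = 15.6 points for the same number of clinics, nearly the same control proportion and similar power, so the two documents describe one design with materially different detectable effects.

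**Working it through.** **Inputs.** From Protocol 9.2: control proportion p0 = 0.64, intervention proportion p1 = 0.88, ICC = 0.055, c = 14 clinics per arm, m = 50 to 100 per clinic. Losing two clinics is taken as c = 13 per arm. From Protocol 9.4.2: two-sided 5% test.

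**Formula.** Design effect D = 1 + (m − 1) × ICC. Effective number per arm n = c × m / D. Standard error SE = √{[p0(1 − p0) + p1(1 − p1)] / n}. Power comes from the noncentral t distribution with 2c − 2 degrees of freedom and noncentrality (p1 − p0)/SE.

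**The stated contrast, 64% versus 88%, m = 50.**
- D = 1 + 49 × 0.055 = 3.695.
- c = 14: n = 700/3.695 = 189.4; SE = √[(0.2304 + 0.1056)/189.4] = 0.0421; noncentrality 0.24/0.0421 = 5.70; critical t (26 df) 2.056; power 99.98%.
- c = 13: n = 650/3.695 = 175.9; SE = 0.0437; noncentrality 5.49; critical t (24 df) 2.064; power 99.95%.

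The stated 83% and 80% are not reproduced, and losing two clinics costs about 0.03 points rather than 3. With m = 100 (D = 6.445) power is above 99.99% and 99.99%.

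**Other methods for the same contrast, m = 50.**

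| Method | 14 per arm | 13 per arm |
|---|---|---|
| Stated in Protocol 9.2 | 83% | 80% |
| Common ICC, t with 2c − 2 df | 99.98% | 99.95% |
| Common ICC, paired t with c − 1 df | 99.95% | 99.89% |
| Beta-binomial simulation, t-test on clinic proportions, 200,000 runs | 99.97% | 99.94% |
| Constant k = 0.176 in both arms | 98.6% | 97.9% |

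Here k = √[ICC × (1 − p0)/p0] = √(0.055 × 0.36/0.64) = 0.176.

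Two further checks show the size of the gap. Five clinics per arm already give 84.6% for 64% versus 88% (m = 50, ICC 0.055). To bring power down to 83% with 14 per arm, or 80% with 13, the ICC would have to be about 0.25, more than four times the stated conservative bound.

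**Which intervention proportion fits the stated pair?** Solving for p1 at ICC 0.055 gives 78.0% at m = 50 and 77.1% at m = 100, the same for both power figures. Check at 78%, m = 50:
- c = 14: SE = √[(0.2304 + 0.1716)/189.4] = 0.0461; noncentrality 0.14/0.0461 = 3.04; power 83.3%.
- c = 13: SE = 0.0478; noncentrality 2.93; power 80.2%. If both lost clinics are intervention clinics (12 against 14), power is 80.4%.
- Simulation: 82.9% and 79.8%.

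With constant k = 0.176 instead, the pair falls at about 80.2% (m = 50) or 79.4% (m = 100).

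**Cross-check of SAP 7.2.** The clustered-proportions formula is c = 1 + (z_α/2 + z_β)² × V / (p1 − p0)², where V = p0(1 − p0)/m + p1(1 − p1)/m + k²(p0² + p1²). With p0 = 0.65, p1 = 0.806, m = 50 and k = 0.175, V = 0.00455 + 0.00313 + 0.03283 = 0.0405. With c = 14, z = 0.156/√(0.0405/13) = 2.79 and power is 79.8%. The SAP's figure reproduces.

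The two clustering inputs agree in the control arm only. Converting k = 0.175 by ICC = k² × p/(1 − p) gives 0.057 at 65% but 0.127 at 80.6%. At ICC 0.055 the SAP's contrast has 91.5% power.

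**The case against.** The strongest reply is that 83% is offered as a minimum, and 99.98% does exceed it. That saves the first figure in a literal sense. It does not save the second, which says without qualification that 80% power is retained for 64% versus 88%. The two figures together read as near-actual power.

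A second objection is that 78% depends on the method. This is correct. A paired analysis, which the pairing in Protocol 6.3 and Appendix 1 could suggest, gives 80.2% and 76.7% at 78%. Constant k gives 71.8% and 68.4% there and moves the matching value to about 79-80%. Nor do the two stated figures confirm 78% twice over: going from 14 to 13 clinics per arm costs about three points at whatever proportion first gives 83%. So 78% is the match at the protocol's own ICC with an unpaired t-test and 50 per clinic. It is not proof of what the authors calculated. What stands under every method is that 88% is not the match.

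A third objection is that little follows in practice. Enrolment, conduct, estimator and test do not depend on the sentence, and SAP 7.2 supplies a calculation that reproduces. That limits the consequence, but the SAP neither corrects nor withdraws Protocol 9.2.

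**Conclusion.** The concern holds. At 64% versus 88% with 50 per clinic, the protocol's inputs give 99.98% power (14 per arm) and 99.95% (13 per arm), against the stated 83% and 80%. The lowest result from any 5%-level method tried is 97.9%. At ICC 0.055 the stated power corresponds to a gain of about 14 points (64% to 78%), not 24.

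This rests on the two-sided 5% level from Protocol 9.4.2, an even loss of the two clinics (an uneven loss barely changes the answer) and equal clinic sizes. A one-sided test would only raise power. The documents do not show whether 88% is a misprint or comes from another calculation. The error understates the design's sensitivity; it does not reveal a shortfall in sample size.

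**What to change.** Go back to the source calculation and restate Protocol 9.2 so that the intervention proportion, power, clustering input and alpha agree, with alpha and sidedness written out. There are two coherent forms:

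- **Correct the proportion.** If 83% and 80% are the intended power figures, give the intervention proportion that yields them: about 78% at ICC 0.055 with 50 per clinic.
- **Keep 88%.** Restate power as above 99% at ICC 0.055, with and without the loss of two clinics. If the clustering input is changed to constant k, this should read about 98%.

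An intervention proportion near 80% fits the stated power only if the clustering input also becomes constant k, because ICC 0.055 gives 92.4% and 90.3% at 80% (50 per clinic).

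Then reconcile the target effect and the clustering measure (ICC or k) with SAP 7.2, or say why they differ. The cost is wording only, with no change to enrolment, conduct or analysis.
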